AZOD530's blockade will act to “reset” dopaminergic imbalance in extended reward system circuitry of FHP so that abnormal NAcc, ACC, and DLPFC activation during response inhibition will be normalized and more closely resemble that of matched FHN individuals in the placebo condition.

Importance: tests hypothesis of DA/NMDA imbalance in response inhibition circuitry as a risk factor for alcoholism. Logical extension of data gathered in prior phase of CTNA.

Extended network analysis using functional connectivity approaches will show interrelationships among neural circuits responsible for response inhibition (GNG) and motivation (MID) and additionally their alteration by Saracatinib in FHP (exploratory).

3. AZ0D530 trial with fMRI Alcohol Cue Reactivity (ACR) task (AKA ‘NAC’ task). The ACR task in alcohol users is related to the brain's response in reward-related regions to wanting and craving of alcohol versus matched soft drink stimuli. Prior data also suggest that Saracatinib will suppress cue-induced alcohol craving, perhaps more markedly in FHP. **Aim:** to examine NAcc response to alcohol-related versus control images using an existing ACR task.

Major hypothesis. FHP who use alcohol will respond with greater NAcc BOLD signal to alcohol-related cues vs. non-alcohol cues than matched FHN who use alcohol. **Subsidiary hypothesis.** Alcohol-using subjects in general will show a reduced response to alcohol images in the ACR task during the Saracatinib condition, but more markedly in FHP.

Importance: examines additional forms of responsiveness likely relevant to initiation into alcohol misuse.

4. Pilot Task: Pavlovian-to-Instrumental Transfer (PIT) Elaboration of MIDT

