The primary outcome for this Aim will be BOLD activation during the A1 phase of the MID task. The effects of Saracatinib treatment on activation will be assessed using linear mixed models. In these models, BOLD response will represent the dependent measure and family history status (FHP vs. FHN) will represent a between-subjects explanatory variable, while treatment (placebo vs. Saracatinib) and ROI (NAcc vs. OFC) will be included as within-subjects factors. All 2-way interactions will be modeled and interpreted using graphical displays and appropriate post-hoc tests. In the above analysis, we anticipate a family history by treatment by ROI interaction explained by significant NAcc decreases and significant OFC increases in BOLD response due to Saracatinib treatment among FHP subjects. Secondary analyses will include the above analysis performed for activation levels observed during the A2 phase and examination of additional ROIs as well as dose and. Similar models as described, excluding phase as a factor, will be used to model BART and EDT outcomes (subsidiary hypothesis). In these models, we expect a family history by treatment interaction such that each of these impulsivity measures are reduced by Saracatinib treatment among FHP individuals.

Aim 2

BOLD signal activation in the anterior cingulate cortex (ACC) observed during False Alarms of the GNG task will represent the primary outcome in this Aim. The effects of Saracatinib treatment on activation will be assessed using linear mixed models with family history (FHP vs. FHN) included as a between-subjects factor and treatment (placebo vs. Saracatinib) and response type (false alarms vs. correct rejections) as within-subjects factors. A significant family history by treatment by response type interaction explained by increased BOLD activation due to Saracatinib during false alarms in both groups, but more markedly in FHN, will be supportive of our hypothesis. We will consider other regions (BA9, BA44/45, BA47, Insula, VS) represented as additional within-subjects factors in the model described above. In this analysis, we expect Saracatinib to reduce BOLD signal activation among FHP in each of the regions during correct rejections.

Aim 3

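### Aim 2: the two predicted saracatinib effects pull the named three-way interaction in opposite directions, so where both apply to the same region the support test can be null or reversed although both are true

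*Combined protocol and SAP*

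**What the plan says.** Section 6b, Aim 2 sets the primary outcome: "BOLD signal activation in the anterior cingulate cortex (ACC) observed during False Alarms of the GNG task will represent the primary outcome in this Aim". Its linear mixed model has family history between subjects, and "treatment (placebo vs. Saracatinib) and response type (false alarms vs. correct rejections) as within-subjects factors". The criterion for support opens "A significant family history by treatment by response type interaction explained by" and is completed by the expected pattern: "increased BOLD activation due to Saracatinib during false alarms in both groups, but more markedly in FHN, will be supportive of our hypothesis".

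The paragraph then widens the model: "We will consider other regions (BA9, BA44/45, BA47, Insula, VS) represented as additional within-subjects factors in the model described above". For that analysis it adds a second prediction: "we expect Saracatinib to reduce BOLD signal activation among FHP in each of the regions during correct rejections". It does not say whether the ACC is among those regions. It predicts nothing for FHN on correct rejections, gives no magnitudes, and names no separate test of either prediction.

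Section 4, hypothesis 2 expects that in FHP "abnormal NAcc, ACC, and DLPFC activation during response inhibition will be normalized and more closely resemble that of matched FHN individuals", with FHN on placebo as the comparator. It names the ACC but gives no direction of change.

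**The concern.** A three-way interaction here is a difference between two family history × treatment effects: the one on false alarms minus the one on correct rejections. It suits a hypothesis in which the two response types differ in that effect. The plan's predictions do not clearly describe such a difference. On false alarms the drug is expected to raise activation less in FHP than in FHN. On correct rejections it is expected to lower activation in FHP. Both make the drug effect in FHP lower than in FHN, provided FHN do not fall as much on correct rejections. Subtracting one from the other then removes part or all of what the investigators expect to see.

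The study is meant to assess effect sizes (section 5.1) and to inform the power of later studies (section 6). A difference between two predicted effects estimates neither of them. The declared primary outcome is activation during false alarms, yet the result that counts as support has correct rejections subtracted from it.

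**Working it through.** **Inputs from the documents.** 45 FHP and 45 FHN, each measured on drug and placebo (sections 1 and 5.2). The predicted directions come from section 6b, Aim 2. The plan states no power, effect size, SD or alpha level for this aim, so there is no figure to reproduce.

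**Contrast.** Write each effect as saracatinib minus placebo.

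- False alarms: +a in FHP and +b in FHN, with b > a > 0.
- Correct rejections: −c in FHP, with c > 0, and e in FHN (no prediction given).

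The three-way contrast is

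L = [a − (−c)] − [b − e] = −(b − a) + c + e.

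The false-alarm prediction contributes −(b − a), which is negative. The correct-rejection prediction contributes +c. They offset each other when c + e > 0, that is, when FHN do not fall as much as FHP. L is exactly zero when c + e = b − a, and it is positive (reversed) when c + e > b − a.

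**Assumptions for the illustration.** The drug-minus-placebo difference within one response type has SD 1. The correlation ρ between the false-alarm and correct-rejection differences is 0 or 0.5. The test is two-sided at 5%, with b − a = 0.6.

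**Power.** The SD of a subject's double difference is √(2 − 2ρ), which is 1.414 at ρ = 0 and 1 at ρ = 0.5. The noncentrality is (|L| / SD) × √(45/2), with 88 degrees of freedom. For c = 0.3 and e = 0, |L| = 0.3, so the noncentrality is 0.212 × 4.743 = 1.01 at ρ = 0 and 0.3 × 4.743 = 1.42 at ρ = 0.5.

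| c | e | L | Power, ρ = 0 | Power, ρ = 0.5 |
|---|---|---|---|---|
| 0 | 0 | −0.60 | 51% | 80% |
| 0.3 | 0 | −0.30 | 17% | 29% |
| 0.45 | 0 | −0.15 | 8% | 11% |
| 0.6 | 0 | 0 | 5% | 5% |
| 0.9 | 0 | +0.30 | 17%, reversed | 29%, reversed |
| 1.2 | 0 | +0.60 | 51%, reversed | 80%, reversed |
| 0.6 | −0.3 | −0.30 | 17% | 29% |
| 0.6 | −0.6 | −0.60 | 51% | 80% |

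The 5% at c = 0.6 is simply the type I error rate. A 20,000-run simulation at ρ = 0 with e = 0 agrees: 51%, 17%, 5% and 53% for c = 0, 0.3, 0.6 and 1.2.

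**Direct tests under the same assumptions.**

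- Family history × treatment within false alarms, effect 0.6: noncentrality 0.6 × 4.743 = 2.85, power 80% (71% at alpha 0.025).
- Drug effect on correct rejections within FHP, c = 0.6, n = 45: noncentrality 0.6 × √45 = 4.02 on 44 degrees of freedom, power 98% (95% at alpha 0.025).

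**The case against.** The strongest objection is that the text does not clearly place both predictions in one region. The support criterion is set out for the ACC. The correct-rejection prediction follows the list of five added regions, and those are its nearest antecedent. On that reading the ACC test is not weakened at all. Hypothesis 2 names the ACC during response inhibition, and the added regions join the same model, so including the ACC is plausible. But hypothesis 2 gives no direction and Aim 2 does not settle the matter. The objection therefore stands as a condition on the point.

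Second, the plan is silent on FHN during correct rejections. If FHN fall as much as FHP (e = −c), the FHP prediction is true and nothing is offset. Restricting the prediction to FHP, straight after one made for both groups, suggests a difference but does not state one. A partial FHN fall still leaves a weak test, as the row with e = −0.3 shows.

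Third, the same model contains the family history × treatment term averaged over response types. With b − a = c = 0.6, e = 0 and ρ = 0.5, that effect is −0.6 with SD √((1 + 0.5)/2) = 0.866, and power is about 90%. The signal is thus in the data, but Aim 2 does not name that term as support.

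A reader might go on to infer that a null interaction commits the sponsor to declaring Aim 2 unsupported. The plan says only that a significant interaction would be supportive. It does not say what its absence means.

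**Conclusion.** The point holds conditionally. The opposite signs follow from the plan's own predictions and need no outside figure. The offset in the ACC test rests on two conditions: the correct-rejection prediction covers the ACC, and FHN do not fall as much as FHP on correct rejections. Where both are met, the only result named as supportive can be null or reversed while both predictions are true.

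Two stronger readings are tempting and unsupported. One is that the effects must cancel. Full cancellation needs c + e = b − a, and the documents give no magnitudes. The other is that the interaction is well powered only if the correct-rejection prediction is false. At ρ = 0.5 it also reaches 80% when c = 1.2, with the sign reversed, or when FHN fall as much as FHP.

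The size is illustrative because the effect sizes, SD, correlation and alpha are all assumed. With b − a = 0.6 and e = 0, power is at most 29% for every c from 0.3 to 0.9, at either correlation.

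**What to change.** In section 6b, Aim 2:

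1. Make family history × treatment within false alarms in the ACC, the declared primary outcome, the support criterion for the false-alarm prediction.
2. Test the correct-rejection prediction separately as the saracatinib-minus-placebo effect within FHP, which is what the plan predicts. Report family history × treatment within correct rejections alongside it.
3. Share alpha between the two tested contrasts, for example by Holm, and say how this fits with the Bonferroni correction across regions of interest in section 6a.
4. Report each estimate with its confidence interval, and keep the three-way interaction as a descriptive check on whether the response types differ.
5. State whether the correct-rejection prediction covers the ACC, and what is expected in FHN on correct rejections.

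The cost is wording only; the data and the model stay the same. Sharing alpha loses some power: under the assumptions above, at alpha 0.025, from 80% to 71% for the false-alarm contrast and from 98% to 95% for the within-FHP contrast. Holm loses no more than that for these two contrasts. Any further correction across regions would come on top.

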Saracatinib effects on this task will be explored with support of the Clinical Core to reinforce efforts of other projects to dissect the role of Fyn in the striatal direct (D1-R) and indirect (D2-R) pathways ^{141,142}

Major hypothesis: Deficient learning of negative reward contingencies (i.e., punishment) will be associated with reduced dorsal striatum activation in FHP compared to FHN due to deficits in D2-R signaling and downstream enhancement of NMDA-R signaling. Reducing NMDA-R signaling with Saracatinib is predicted to normalize, relative to FHNs, the striatal activation during punishment learning.

6. Functional Connectivity.

Using approaches developed by the Human Connectome Project and imported into CTNA via the Translational Technologies Core, we will explore brain functional connectivity during rest and during task (within and across tasks).

Major hypothesis: We propose to replicate increased functional connectivity of the NAc in FHP compared to FHN, as reported by other groups^{143,144}. We propose to determine whether Saracatinib normalizes NAc functional connectivity in FHP, which would suggest that enhanced signaling via Fyn and NMDA-R contribute to the distinct patterns of NAc functional connectivity in the two groups.

EKG: Screening day and subsequent drug administration days- Obtained at request of drug manufacturer (A-Z) for screening and safety monitoring.

Blood Tests: Screening and each subsequent experimental day (at end of the session); CBC, liver function, electrolytes, B12, - obtained per A-Z for study safety monitoring purposes.

5. METHODS:

5.1 Research design and sample size/statistical power:

Saracatinib has not previously been used in this context. The purpose of the current study is to assess the effect size of interventions with this medication compared to placebo.

5.2 Subjects:

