Subjects will either have a family history of alcoholism (FHP) or no family history of alcoholism (FHN; N=45 per group, to a total of 90 subjects; males and females in equal numbers). We will recruit subjects from the general population by advertisement (e.g. in the Hartford Advocate or on Craig's List). Yale University will provide and pay for an encrypted, password-protected study cell phone to contact potential subjects via text message. Subjects will also have the opportunity to agree to text message appointment reminders in the informed consent form. Interested participants will also have the chance to respond to web based advertisements that include the option to call in to be screened for eligibility over the telephone or via a locked online survey database. If participants complete the online pre-screener and are found eligible they will then be contacted to be fully screened by the staff recruiter to determine complete eligibility.

The CTNA study coordinator screens all potential subjects obtained from the above sources, and a study FH status is determined using the family history approach operationalized by the Family History Assessment Module (FHAM), developed by COGA. FHPs are defined as having a parent and at least another first- or second-degree relative with alcohol dependence OR having at least a father with a history of alcoholism. If the affected parent is the mother, we will rule out possible fetal alcohol syndrome, using a standardized symptom checklist; FHN will have no affected first-degree relative. We will be selecting subjects from families with substantial risk for developing alcoholism, and this increased susceptibility probably reflects increased genetic liability.

5.3a Inclusion Criteria:

Inclusion criteria are equal numbers of men and women between the ages of 18 and 40 years. Recruitment will be through advertisement. On each test day, subjects will be first screened toxicologically for drugs of abuse (and for women of childbearing age, pregnancy) by urine testing, any positive test results in exclusion. Our participants will not come from a "vulnerable population" because participants will not be pregnant women, under legal coercion or restriction,

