Subjects may find the battery of psychiatric and psychological tests tedious and boring, or intrusive. If the former is the case, additional brief breaks will be given during assessment. The latter concern is addressed through use of trained interviewers who have experience discussing sensitive material with clinical research subjects. However, if a subject finds a topic too uncomfortable, those questions will be skipped, or with severe reactions, subjects will be reminded they can discontinue participation without penalty.

Following study completion, subjects will only be allowed to be discharged when they have minimal subjective reports of intoxication or sedation, their vital signs have returned to baseline, and they have been assessed by either an RN or physician.

MRI:

The FDA has approved the MRI system and the scanning protocols to be used. The MRI scanning procedure in a 3 Tesla system is safe in normal healthy humans. However, subjects who could suffer potential risks from the MRI scanning procedure include those with metal implants (pacemaker, metal rods, bone screws, orthodontics, metal flakes from metalworking). Subjects are told during the informed consent process about the need to carefully screen for metal implants or any other exposure to metal in the body. Subjects who could potentially suffer harm will be screened for metal prior to scanning using a HH Radiology Department screening checklist. Although there is no proven harm to developing fetuses, women will be screened for pregnancy before scanning. Subjects with claustrophobia may experience some anxiety symptoms, and will be discouraged from participating. Subjects who feel claustrophobic during the experiment will be encouraged to notify experimenters at any time to discontinue scanning. There are no known risks associated with the visual or auditory stimuli presented during recording of event-related fMRI.

Structural MRI: Performed on day 1 only.

Functional MRI tasks: (both study days)

The Monetary Incentive Delay (MID) Task:

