Linear mixed models will be used to evaluate the effects of family history on NAcc BOLD response during the ACR task. These models will include family history (FHP vs. FHN) as a between-subjects factor and type of Cue (ETOH-related vs. non-EOTH) as a within-subjects factor. We anticipate a significant group by cue interaction such that FHP subjects will respond with greater NAcc BOLD signal to alcohol-related cues vs. non-alcohol cues compared to matched FHN subjects and subsequently experience a greater reduction in NAcc BOLD response following Saracatinib administration.

Aim 4

The same statistical models described for Aim 1 will be used to evaluate the effects of Saracatinib and family history on NAcc and OFC activation during the A1 phase of the PIT-in

modified MID task. In these models, however, we will include Cue Type (PIT-related vs. Non-PIT-related) as an additional within-subjects variable. We expect a significant family history by treatment by cue type by region interaction explained by significant NAcc decreases and significant OFC increases in BOLD response due to Saracatinib treatment among FHP subjects, with these effects most exaggerated during the presentation of PIT-related cues. In addition, using regression we can test whether PIT responses (using the out-of-scanner version used in all data from study 126237) show the expected learning effect.

7. Risks and Data Monitoring Plan:

Under some circumstances, it can be a risk for genetic information about subjects to be known. Variation in some genes is known to be directly related to risk for certain illnesses. Other genes we will be studying in subject DNA may be shown at some point in the future to be related to illnesses. Since the results of these genetic tests may allow prediction of risk of illness in some cases, we will make every effort to keep the results confidential (only scientists working on this research project will know the results). We will not make any of our laboratory results available to subjects, nor will we add them to any medical record or release them to others.

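### The Aim 3 model for the alcohol cue task has no treatment factor, so it cannot estimate the saracatinib effect that the same aim predicts

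*Combined protocol and SAP*

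**What the plan says.** Section 6b, Aim 3 sets out linear mixed models for the effect of family history on NAcc BOLD response in the alcohol cue reactivity (ACR) task. The factors are given in one sentence: "These models will include family history (FHP vs. FHN) as a between-subjects factor and type of Cue (ETOH-related vs. non-EOTH"), the latter within subjects. The paragraph expects a group by cue interaction, and then that FHP subjects will "subsequently experience a greater reduction in NAcc BOLD response following Saracatinib administration".

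Section 4, hypothesis 3 has two parts. The major hypothesis is that "FHP who use alcohol will respond with greater NAcc BOLD signal to alcohol-related cues" than matched family-history-negative (FHN) subjects who use alcohol. The subsidiary hypothesis is that alcohol users in general will show a "reduced response to alcohol images in the ACR task during the Saracatinib condition, but more markedly in FHP".

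Three other places bear on this:
- Section 5.1: "The purpose of the current study is to assess the effect size of interventions with this medication compared to placebo".
- Section 5.4, under MRI: "Functional MRI tasks: (both study days").
- Section 5.3a: "Inclusion criteria are equal numbers of men and women between the ages of 18 and 40 years". Neither 5.3a nor 5.3b requires that a subject drink.

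Aims 1 and 2 in Section 6b both list treatment (placebo vs. saracatinib) as a within-subjects factor.

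**The concern.** A model without treatment cannot estimate a treatment effect or compare one between groups. Both drug predictions for the ACR task are therefore left without an analysis, in a study whose stated purpose is to size the drug effect. Whoever analyses the data would have to choose a model for those predictions after the fact.

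The omission also affects the family history by cue test that the model does contain. Each subject is scanned once on placebo and once on saracatinib, and the plan does not say whether one session or both enter. If the drug acts as predicted, the two choices estimate different quantities.

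Finally, Section 4 limits both hypotheses to subjects who use alcohol. Aim 3 does not repeat the limit and the entry criteria do not impose it, so the analysis population and its size are unstated.

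**Working it through.** The plan gives no effect size, SD, alpha or power for this aim, so there is no figure to reproduce. The check is a count of model terms and a short calculation on assumed effects.

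**1. Which terms are present.** Family history (2) × treatment (2) × cue (2) gives 8 cell means, so a full model has 8 fixed-effect parameters.

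| Term | In the Aim 3 model | Needed for |
|---|---|---|
| Intercept, family history, cue | yes | – |
| Family history × cue | yes | major hypothesis |
| Treatment | no | subsidiary, first part |
| Treatment × cue | no | subsidiary, first part, relative to control images |
| Family history × treatment | no | subsidiary, second part |
| Family history × treatment × cue | no | subsidiary, second part, cue-specific |

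The stated model has 4 of the 8 parameters and none of the 4 that involve treatment.

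**2. Whether another section supplies them.** Section 6a has a general paragraph on treatment differences in regions of interest, and NAcc is among its primary regions. It describes a pre- to post-treatment comparison on a symptom provocation task with owned and control items. That is not the ACR task, and the paragraph does not alter the Aim 3 model.

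**3. What the session choice does to the family history × cue estimate.** Assume an FHP excess of 0.60 SD in the cue contrast on placebo, and let the drug remove a share f of it.
- Placebo session alone: 0.60, whatever f is.
- Both sessions pooled with no treatment term: [0.60 + 0.60(1 − f)]/2 = 0.60(1 − f/2).

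| Share removed, f | Placebo session | Pooled |
|---|---|---|
| 0 | 0.60 | 0.60 |
| 0.5 | 0.60 | 0.45 |
| 1 | 0.60 | 0.30 |

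Pooling also reduces noise. With equal session SDs and between-session correlation r, the pooled standardised effect is 0.60(1 − f/2)/√((1 + r)/2). It exceeds the single-session 0.60 when f < 2(1 − √((1 + r)/2)), which is 0.39, 0.27 and 0.16 for r = 0.3, 0.5 and 0.7. So pooling can gain power when the drug does little. The objection to it is that the target changes with the drug effect.

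**4. What the added terms could show.** Use SD units of the subject-level drug-minus-placebo difference, with two-sided 95% intervals. The planned 45 per group (Section 5.2) is an upper limit if only alcohol users count; 35 and 25 are assumed.
- FHP versus FHN difference in drug effect: half-width t(0.975, 2n − 2) × √(2/n) = 0.42, 0.48 and 0.57 at n = 45, 35 and 25 per group. Power for an assumed 0.4 SD difference is 47%, 38% and 28%.
- Drug effect over both groups: half-width t(0.975, 89)/√90 = 0.21 at 90 subjects. One-sample power for an assumed 0.4 SD is 96%, 91% and 79% at 90, 70 and 50 subjects.

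The two parts of the subsidiary hypothesis therefore differ greatly in precision and should be reported separately.

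**The case against.** The strongest reply is that Aim 3's model is stated as one for family history effects and matches the major hypothesis. The drug prediction is subsidiary, and Section 6a plans treatment comparisons in NAcc. The first part stands: a reader might infer that Aim 3 fails as a whole, and it does not, because family history × cue is in the model. The appeal to Section 6a fails because that text concerns a different task.

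A reader might also infer that Aims 1 and 4 share the defect, since the only interaction order stated is "All 2-way interactions will be modeled and interpreted using graphical displays and appropriate post-hoc tests", which Aim 4 takes over by reference, while the expected results are a three-way and a four-way interaction. The documents do not support that. The sentence does not say that only two-way terms are modeled, and Aim 1 goes on to name the three-way interaction as expected in that very analysis. Aim 4 likewise gives the four-way term as its expected result. Bias figures for a model restricted to two-way terms would describe a model the authors show no sign of intending. Only a wording clarification remains. Aim 2 lists treatment, sets no limit on interaction order and is not affected.

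**Conclusion.** The point holds for Aim 3 and should be fixed. As written, Aim 3 yields no estimate of the saracatinib effect on the ACR task, and so none of whether that effect is larger in FHP. This follows from the list of factors and rests on no numerical assumption.

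The size of the session problem does rest on assumptions: a 0.60 SD placebo excess would be reported as 0.45 or 0.30 SD under pooling if the drug removes half or all of it, and as 0.60 SD if it removes none. The plan does not say that sessions will be pooled, so this is a consequence of one open choice and not a certain bias. The major hypothesis remains testable.

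**What to change.** In Section 6b, Aim 3:
- Add treatment and all its interactions with family history and cue, and fit the model to both sessions.
- Test the major hypothesis as the family history × cue contrast in the placebo session.
- Test the first part of the subsidiary hypothesis (alcohol users in general) with the treatment effect on alcohol images, or treatment × cue, averaged over the two groups. State which. The three-way term does not test this part.
- Test the second part (more marked in FHP) with family history × treatment on alcohol images, and give family history × treatment × cue as the cue-specific version.
- Apply Section 4's limit to subjects who use alcohol, define it, and report how many subjects it leaves per group.

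As a wording note only, in Aim 1 (and so Aim 4) replace the two-way sentence with the full factorial, so that the three-way and four-way terms already expected are listed.

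The cost is a few lines of text and four more fixed-effect parameters in Aim 3 (8 instead of 4). No new data are needed, because the tasks already run on both study days.

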Brain responses to the prospect of reward (A1) phase of the MIDT may be considered to reflect a process of Pavlovian-to-Instrumental Transfer (PIT); that is, the phase of the task following the trial-type cue but before the imperative stimulus indicates the impending necessity for a speeded instrumental response in order to gain a reinforcer; a process that we hypothesize is functionally equivalent to PIT. The enhanced striatal responding during this phase that we observed in FHP in pilot data strongly suggests that aberrations of the effects of cues on instrumental choice may underpin the increased risk of alcoholism observed in the FHP group. We propose to test this hypothesis with a novel **fMRI PIT MIDT**. Outside of the scanner, we will train Pavlovian predictors of monetary reinforcement; color-based visual cues that predict monetary reward irrespective of the subject's behavior. Within the scanner we will superimpose these cues on the A1 (reward prospect) phase of the MIDT fMRI task, e.g. the "Win \$5" notification could be colored with a predictor shade of e.g. red. If neural response to cues signaling reward are "PIT-driven," then Pavlovian predictors of monetary reward should further invigorate behavioral and neural responding, ie fMRI BOLD signal in reward areas will increase further. Such a finding would link our current project aims by identifying a neural mechanism that bridges cue reactivity and reward system-related impulsivity branches of alcoholism to neurobiological vulnerability research.

Major hypothesis: Cues that predict monetary reward will act as Pavlovian incentive stimuli, enhancing striatal responding during fMRI MIDT A1 phase, and by decreasing reaction-time to imperative stimuli. We expect this effect to be stronger in FHP than FHN and related to our second impulsivity factor that consists of scores on the Sensitivity to Punishment/Sensitivity to Reward Questionnaire (SPSRQ) and Padua inventory.

Importance: This task dissects a component of the MID, testing the hypothesis that A1 responding is a form of PIT. Moreover, it provides an imaging assay of a transfer-like process that can be related to real-world drinking behavior, thus informing upon and extending the key finding from CTNA-2.

Exploratory Aims:

5. Probabilistic Selection fMRI task (PST).

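### Aim 4 names a four-way drug interaction as its expected result, but Hypothesis 4 predicts cue and family history × cue effects, and its reaction-time and impulsivity-factor predictions have no analysis

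*Combined protocol and SAP*

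**What the plan says.** **Hypothesis.** Item 4 of section 4 (Major Hypotheses) is headed "4. Pilot Task: Pavlovian-to-Instrumental Transfer (PIT) Elaboration of MIDT". The headings of items 1 to 3 each present the item as a trial of the drug; this one does not. The hypothesis reads: "Cues that predict monetary reward will act as Pavlovian incentive stimuli, enhancing striatal responding during fMRI MIDT A1 phase, and by decreasing reaction-time". It continues: "We expect this effect to be stronger in FHP than FHN and related to our second impulsivity factor", the factor being made up of SPSRQ and Padua scores. Neither Saracatinib nor OFC appears in it. The stated importance of the task is to test whether A1 responding is a form of PIT.

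**Analysis.** Section 6b, Aim 4, reuses the Aim 1 models to "evaluate the effects of Saracatinib and family history on NAcc and OFC activation during the A1 phase" and adds cue type as a within-subjects variable. It then says: "We expect a significant family history by treatment by cue type by region interaction". The pattern that it gives for this result is "significant NAcc decreases and significant OFC increases in BOLD response due to Saracatinib treatment among FHP subjects", largest for the PIT cues. The one further analysis is optional: "using regression we can test whether PIT responses (using the out-of-scanner version used in all data from study 126237) show the expected learning effect".

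**Inherited model.** Section 6b, Aim 1, has family history between subjects, and treatment and ROI (NAcc, OFC) within subjects. The only interactions that it says will be modelled are the two-way ones.

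**The concern.** The hypothesis concerns what the cues do and whether they do more in FHP. The result named in the analysis concerns what the drug does to a regional difference in that group effect. These are different estimands. A true PIT effect could leave the named test null, and a significant result on the named test would not show a PIT effect. Two predictions (faster reactions, and the link to the impulsivity factor) also appear to have no analysis. If so, the choice of test for Hypothesis 4 would be made after the data are seen.

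**Working it through.** The plan gives no figure to reproduce here beyond 45 + 45 = 90 subjects (section 5.2). The check is mainly a comparison of texts.

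**1. Predictions against analyses**

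| Hypothesis 4 predicts | Analysis in the plan |
|---|---|
| Cue effect on striatal A1 BOLD | Cue type is in the Aim 4 model, but is not named as the test |
| Larger cue effect in FHP than FHN | Family history × cue is in the model as a two-way term, but is not named and is not region-specific |
| Shorter reaction time | None found |
| Relation to the SPSRQ/Padua factor | None found |

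Reaction time is mentioned for the ACR task (logged for analysis) and for the out-of-scanner Go/No-Go task, but not for the PIT-MID. The behavioural outcomes modelled in section 6b are BART and EDT (Aim 1). SPSRQ and Padua are listed among the paper measures in section 5.4, and no analysis uses them.

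**2. What the four-way contrast measures**

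Let D(t, r) be the FHP minus FHN difference in the cue effect (PIT minus non-PIT cue) under treatment t in region r. Write S for Saracatinib and P for placebo. The four-way contrast is

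[D(S, NAcc) − D(P, NAcc)] − [D(S, OFC) − D(P, OFC)].

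Suppose the effect is the same in both sessions, which a hypothesis without a drug term allows. Put D = δ in NAcc and D = ε in OFC. The contrast is (δ − δ) − (ε − ε) = 0 for every δ and ε, so the test rejects only at its alpha level.

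Conversely, take D(P, NAcc) = 0, D(S, NAcc) = −k and no OFC effect. The contrast is −k, which can be significant with no group difference in cue response on placebo.

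**3. What the two-way model gives**

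With two-way terms only, family history × cue has one coefficient, shared by both regions and both treatments. In complete, balanced data it estimates (δ + ε)/2, which is δ/2 if the effect is confined to NAcc. The NAcc cue effect averaged over groups can be recovered from cue plus cue × region. The group difference in NAcc cannot be recovered. The four-way term is not in this model at all.

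**4. Precision (illustration only)**

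Assumed, not in the documents: two-sided alpha 0.05, 80% power, normal approximation, and independent cell residuals of equal variance s². The smallest detectable group difference is (1.960 + 0.842) × √(2/45) = 0.59 SD of the per-subject contrast. In units of s:

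| Contrast | Variance | 80% power | 90% power |
|---|---|---|---|
| Family history × cue, NAcc, both sessions averaged | 1 s² | 0.59 | 0.68 |
| Same, placebo session only | 2 s² | 0.84 | 0.97 |
| Four-way | 8 s² | 1.67 | 1.93 |

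The four-way contrast has √8 = 2.8 times the standard error of the first. These are different quantities, so the table compares precision and not power for one common effect.

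**The case against.** The strongest reply is that the BOLD part of Hypothesis 4 is already covered. Aim 4 adds cue type to a model in which two-way interactions are fitted, so cue and family history × cue will be estimated, with post-hoc tests available. A reader might infer from the mismatch that the BOLD prediction goes wholly untested; the documents do not support that. What remains is that neither term is named as the test, and the group term cannot be specific to NAcc.

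The two-way wording may also be shorthand, since Aim 1 itself anticipates a three-way interaction. If a full factorial model is intended, the NAcc contrast becomes estimable but is still not named.

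Second, this is a drug study. Section 5.1 gives its purpose as estimating the effect size of the medication against placebo, and Aim 4 opens with the drug. A reader might infer that the treatment term does not belong; that also goes too far. It is a legitimate question that Hypothesis 4 does not state.

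Third, the task is labelled a pilot and no power basis is given. That makes the point minor. It does not supply the two missing analyses.

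**Conclusion.** The point holds in this form. The result named in Aim 4 is not a test of Hypothesis 4, and its contrast is exactly zero if the hypothesised effect does not differ between Saracatinib and placebo. The model as written gives no NAcc-specific family history × cue test and omits the four-way term that it expects. Two of the four predictions have no analysis. This rests on the text and on the algebra in steps 2 and 3; the precision figures depend on assumed inputs and are not needed for it.

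Three further inferences are not supported:

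- A power figure for the four-way test cannot be read as the chance of detecting Hypothesis 4. With no drug modification there is nothing for that test to detect, and the documents give no variance, alpha or target effect.
- Nothing requires the test to use the placebo session alone. If the drug does not alter the effect, that discards half the data.
- The documents do not show that every needed variable is in hand. No text says that PIT-MID reaction times are logged or how the factor score is formed.

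The matter is minor, but it decides whether this task can answer its own stated question.

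**What to change.** In section 6b, Aim 4:

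- Include interactions up to the four-way term in the BOLD model.
- Name the NAcc-specific cue contrast and family history × cue contrast as the tests of Hypothesis 4. Estimate them from the model using both sessions, and report the placebo-session estimates alongside.
- Fit the same model, without region, to PIT-MID reaction time, after the sponsor confirms that it is logged.
- Regress each subject's NAcc cue effect on the SPSRQ/Padua factor score, and state how the score is derived.
- Keep the four-way term as a separate drug question. Either add a drug prediction to Hypothesis 4 or label the term secondary.

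The cost is revised wording, a little more analysis work and a few more tests for a pilot task. If reaction times are not logged, that prediction should be marked as not testable in this study.
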